## **STATISTICAL ANALYSES**

Intention-to-treat analysis; significance level of 5%.

Statistical analysis performed by IBM® SPSS® Statistics version 24.

Categorical variables compared by Chi-square or Fisher exact test as appropriate. Medians of quantitative variables compared by Mann-Whitney U test. Latency from PPROM to delivery compared by univariate analysis using Mann-Whitney U test and by survival analysis using Kaplan-Meier curve with group stratification.

Sample size for future RCT calculated based on difference between the means of latency time.

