## **OBJETIVE**

We aimed to access the impact of bed rest in latency time to delivery, chorioamnionitis incidence and other maternal and neonatal outcomes in pregnancies complicated by PPROM, thus enabling proper sample size calculation for future powered randomized controlled trial.

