## **STUDY DESIGN**

Pilot unblinded randomized controlled trial (1:1 allocation ratio).

Simple random allocation sequence generated by the investigators and implemented by sequentially numbered sealed envelopes.

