## **SAMPLE SIZE**

Considering future sample size calculation based upon assumed differences between groups regarding latency and infection, we aim a sample of 30 participants.

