## **OUTCOMES**

Maternal outcomes: latency to delivery after PPROM, clinical chorioamnionitis (defined as maternal fever plus leukocytosis and CRP elevation, or as maternal fever plus any two of the following: fetal tachycardia; maternal tachycardia; uterine tenderness; purulent amniotic fluid), cause of pregnancy termination (spontaneous labor, 34th week, adverse occurrence), mode of delivery, placenta abruption, cord prolapse, and thromboembolic events.

Neonatal outcomes: included GA at delivery, birth weight, APGAR score at fifth minute, length of hospitalization, neonatal sepsis, composite adverse pulmonary outcome (need for ventilatory support, respiratory distress syndrome, bronchopulmonary dysplasia), and neonatal death.

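### The analysis plan is almost entirely 5% tests in 30 women: no confidence intervals, no latency SD and no effect measure for infection, so the pilot's planning quantities are incomplete and carry no stated precision

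*Combined protocol and SAP*

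**What the plan says.** The Objective section says: "We aimed to access the impact of bed rest in latency time to delivery", together with chorioamnionitis and other maternal and neonatal outcomes, "thus enabling proper sample size calculation for future powered randomized controlled trial". The Sample Size section gives the rationale as "Considering future sample size calculation based upon assumed differences between groups regarding latency and infection" and then the number: "we aim a sample of 30 participants". Allocation is 1:1 by simple randomisation (Study Design), so about 15 per arm.

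The Statistical Analyses section specifies "Intention-to-treat analysis; significance level of 5" per cent. For binary and other categorical outcomes it says "Categorical variables compared by Chi-square or Fisher exact test as appropriate". Quantitative outcomes are compared by Mann-Whitney U. Latency also gets Kaplan-Meier curves by group, with no test or hazard ratio named. The section closes by saying that the future trial will be sized on the difference in mean latency.

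No confidence interval is mentioned anywhere. No SD of latency, risk difference, risk ratio, hazard ratio or median shift is named. The Outcomes section includes rare harms ("placenta abruption, cord prolapse, and thromboembolic events", and neonatal death among the neonatal outcomes), which fall under the same categorical tests.

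**The concern.** A pilot meant to size a later trial should deliver estimates and their precision. Here one between-arm estimate is planned, the mean latency difference. It comes without the SD needed to turn it into a sample size on means and without an interval to show how far it can be trusted. For infection, the other planning quantity, only a test is specified.

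The tests themselves carry little information at this size. A non-significant p-value from 15 women per arm does not separate a small effect from a large one, and this matters most for chorioamnionitis and the rare harms. The plan does not say that its p-values are exploratory, nor how a non-significant result is to be interpreted.

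**Working it through.** **Inputs.** From the documents: 30 women, 1:1 (taken as 15 per arm), 5% level (two-sided assumed, as sidedness is not stated). The documents give no event rate, latency SD, effect size or power, so all rates and standardised differences below are assumptions. For the same reason the figure of 30 cannot be reproduced; no stated figure is shown to be wrong.

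**1. Power for binary outcomes.** Exact power is the sum, over all 15 v 15 tables with p < 0.05, of the product of the two binomial probabilities. The plan does not define when each test applies, so the second column uses Fisher if an expected count is below 5 and uncorrected chi-square otherwise.

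| Assumed rates | Fisher | Fisher or chi-square |
|---|---|---|
| 10% v 30% | 15% | 16% |
| 20% v 40% | 11% | 16% |
| 20% v 60% | 45% | 59% |
| 20% v 70% | 68% | 80% |

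**2. Power for latency.** On the normal scale, the difference detectable with 80% power is (1.96 + 0.84) × √(2/15) = 1.02 SD, or about 1.08 SD for Mann-Whitney after allowing for the t distribution and its efficiency. Under simulated skewed latencies (medians 5 to 10 days, follow-up capped uniformly between 0 and 70 days), doubling latency in one arm gives Mann-Whitney power of about 15 to 26%.

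**3. Rare harms.** For k events, all in one arm of a 15:15 split, the two-sided Fisher p is 2 × C(15,k)/C(30,k).
- 4 v 0: 2 × 1365/27405 = 0.0996.
- 5 v 0: 2 × 3003/142506 = 0.042.

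This threshold is not fixed. 7 v 1 gives p = 0.035. Under simple randomisation an exact 15:15 split has probability C(30,15)/2^30, about 14%. At 14:16, four events all in the smaller arm give C(14,4)/C(30,4) = 1001/27405 = 0.037.

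Zero events in 15 women has an exact two-sided 95% upper limit of 1 − 0.025^(1/15) = 21.8%.

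**4. What an interval adds for infection.** Take 3/15 v 8/15 as an illustration. Fisher gives p = 0.13 and uncorrected chi-square p = 0.058, so neither is significant. The risk difference is 8/15 − 3/15 = 0.333. The Wilson limits are 0.301 to 0.752 for 8/15 and 0.070 to 0.452 for 3/15. The Newcombe limits follow:
- Lower: 0.333 − √[(0.533 − 0.301)² + (0.452 − 0.200)²] = −0.01.
- Upper: 0.333 + √[(0.752 − 0.533)² + (0.200 − 0.070)²] = 0.59.

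Equal counts are no more conclusive: 3/15 v 3/15 gives p = 1 and an interval of about ±28 points.

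**5. What an interval adds for sizing on latency.** The half-width of the 95% interval for a mean difference is t(0.975; 28) × √(2/15) = 2.048 × 0.365 = 0.75 SD. Future size per arm at 80% power is n = 2 × (1.96 + 0.84)²/d² = 15.70/d², with d in SD units.
- Observed d = 0.8: n = 25.
- Upper limit, d = 1.55: n = 7.
- Lower limit, d = 0.052: n is about 5,800.

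The pooled SD is itself uncertain. Its 95% limits are √(28/44.46) = 0.79 and √(28/15.31) = 1.35 times the observed value.

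**The case against.** The strongest reply is that the plan is not purely a significance exercise. It does plan a between-arm difference in mean latency, for the first-listed outcome, and it plans Kaplan-Meier curves by group. That stands: a reader might infer that no effect estimate is planned at all, and the Statistical Analyses section contradicts this.

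A reader might also infer that large harms or benefits would be reported as no difference. The documents set no such reporting rule. They call the study a pilot for a later powered trial, and nothing in them withholds the counts behind a test. What can be said is that the plan has no safeguard against that reading.

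Two further strong readings fail. It is not true that the rare-harm tests need at least five events against none: 7 v 1 is significant at 15:15, and 4 v 0 can be at an uneven split. Nor are the tests non-significant almost whatever the truth: power is 68 to 80% for 20% v 70%, and one exponential simulation gave about 63% for a fourfold latency.

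Finally, dropping the tests altogether would be a matter of preference and is not required. None of this supplies the missing intervals, the latency SD or an effect measure for infection. That the study is a pilot makes these more necessary, since they are what a pilot passes on.

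**Conclusion.** The point holds in limited form. Outside Kaplan-Meier curves and one mean latency difference with no SD or interval, the plan specifies only 5% tests, although its declared purpose is to inform a later sample size on latency and infection. At about 15 per arm those tests often miss large effects: Fisher power is 11% for 20% v 40% and 45% for 20% v 60%. They say little about rare harms. The one planned estimate, used alone, could put the next trial at 25 per arm when the data are compatible with anything from 7 to about 5,800.

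The missing elements are plain from the text. The sizes rest on a two-sided 5% level, a 15:15 split and illustrative rates and effects, none of which come from the documents except the 5% and the 1:1 ratio. This is a low-cost improvement that should be made; it does not invalidate the planned tests.

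**What to change.** Amend the Statistical Analyses section as follows.

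- Keep the planned tests and label them exploratory.
- Report latency SD per arm, and the between-arm latency difference (the mean difference, plus a median difference or Hodges-Lehmann shift) with 95% confidence intervals.
- Report the risk difference with a Newcombe or exact 95% interval for chorioamnionitis and the other binary outcomes.
- Report counts per arm with exact 95% limits for abruption, cord prolapse, thromboembolism and neonatal death.
- State that a non-significant result will not be interpreted as absence of effect.
- Carry the intervals for the latency difference, the latency SD and the chorioamnionitis rate into the future sample-size calculation, rather than the point values alone.

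The cost is a few lines of text and slightly more output, with no extra patients or procedures. The downside is that the intervals will be wide and will make it visible that the pilot is inconclusive.

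### Fourteen outcomes share one unadjusted 5% level with no primary outcome, so the chance of at least one false significant result is several times 5% (roughly 20–35% under assumed rates)

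*Combined protocol and SAP*

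**What the plan says.** - **OUTCOMES** gives two lists without ranking. One opens "Maternal outcomes: latency to delivery after PPROM, clinical chorioamnionitis" and continues with cause of termination, mode of delivery, abruption, cord prolapse and thromboembolic events. The other opens "Neonatal outcomes: included GA at delivery, birth weight, APGAR score at fifth minute" and continues with length of stay, sepsis, a pulmonary composite and death. That is 7 + 7 = 14.
- **STATISTICAL ANALYSES** sets the level for everything: "Intention-to-treat analysis; significance level of 5" percent. Tests follow variable type: chi-square or Fisher for categorical outcomes, Mann-Whitney for quantitative ones. Latency is compared both by Mann-Whitney and by Kaplan-Meier curves. The section ends: "Sample size for future RCT calculated based on difference between the means of latency time".
- **SAMPLE SIZE** states only that "we aim a sample of 30 participants", with the later trial's calculation in mind. It mentions latency and infection together.
- **OBJETIVE** aims to assess the effect of bed rest on latency, chorioamnionitis and other outcomes, "thus enabling proper sample size calculation for future powered randomized controlled trial".

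No section names a primary outcome, adjusts for multiplicity or calls the p-values exploratory.

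**The concern.** A plan that fixes a significance level and tests every outcome invites significance claims on any of them. Nothing here says which result counts. The future sample size rests on latency, so latency leads in practice, but it is not labelled primary and the plan does not say which of its two comparisons decides.

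Two things are at stake. First, an isolated p-value below 0.05 among 14 would have no protected meaning. Second, in a trial of 30 women only large observed differences reach 5%, so a significant result will tend to overstate the effect. A pilot meant to inform planning is better served by estimates with their uncertainty, and no confidence interval is planned for any outcome.

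**Working it through.** **The plan's own figures.** It states no overall error rate, and gives no effect size, SD, event rate, power or precision target behind the 30 participants. There is nothing to reproduce, so the check computes the error rate that the stated rule implies.

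**Inputs from the documents.** 5% per test, unadjusted; 30 participants allocated 1:1, taken as 15 per arm (simple randomisation does not guarantee this).
- Five quantitative outcomes: latency, gestational age at delivery, birth weight, Apgar score, length of stay.
- Nine categorical outcomes: chorioamnionitis, cause of termination, mode of delivery, abruption, cord prolapse, thromboembolism, sepsis, pulmonary composite, death.

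**Assumptions not in the documents.** Two-sided tests; cause of termination and mode of delivery treated as binary; these event rates:

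| Outcome | Low | Mid | High |
|---|---|---|---|
| Chorioamnionitis; sepsis (each) | 10% | 20% | 30% |
| Cause of termination | 50% | 50% | 50% |
| Mode of delivery | 30% | 40% | 50% |
| Pulmonary composite | 40% | 50% | 50% |
| Abruption; death (each) | 3% | 5% | 10% |
| Cord prolapse | 1% | 2% | 5% |
| Thromboembolism | 1% | 1% | 2% |

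**Step 1: ceiling.** For 14 independent tests of exact 5% size: 1 − 0.95^14 = 51.2%.

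**Step 2: actual size of the categorical tests at 15 per arm.** Fisher's true size is below 0.1% at event rates of 5% or less, 0.5% at 10%, and 1.6–1.7% at 20–50%. If chi-square is used whenever all expected counts are at least 5, and Fisher otherwise, the size is 1.9% at an event rate of 20%, 2.9% at 30%, 3.9% at 40% and 4.3% at 50%. Rare outcomes add almost nothing.

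**Step 3: combine under independence.** Chance of at least one false positive = 1 − 0.95^5 × Π(1 − s_j), where s_j is the true size of each categorical test and 0.95^5 = 0.774. The five quantitative outcomes alone give 22.6%. For the mid rates:
- Fisher throughout: Π = 0.919, so 1 − 0.774 × 0.919 = 28.9%.
- Chi-square/Fisher mix: Π = 0.847, so 1 − 0.774 × 0.847 = 34.5%.

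Treating the three-level cause of termination at the full 5% adds less than 1 point to the mix and about 2 points to the Fisher-only figures.

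**Step 4: add correlation.** Simulation with 20,000 trials per scenario, one shared latent factor and the chi-square/Fisher mix. Each correlation pair is the value among the quantitative outcomes, then among the latent variables behind the binary ones.

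| Scenario | Low | Mid | High |
|---|---|---|---|
| Independent, Fisher throughout (formula) | 27.2% | 28.9% | 29.7% |
| Independent, mix (formula) | 31.6% | 34.5% | 36.7% |
| Independent, mix (simulated) | 29.2% | 31.9% | 35.9% |
| Moderate correlation, 0.5 / 0.3 | 25.2% | 28.2% | 30.2% |
| Very strong correlation, 0.9 / 0.6 | 16.6% | 19.0% | 20.7% |

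Simulated values under independence sit slightly below the formula because the Mann-Whitney approximation used is a little conservative at 15 per arm: the five tests together rejected in 20–21% of trials, against 22.6%.

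**Step 5: what a significant result must look like.** With 15 per arm, Fisher gives p = 0.0996 for 4 versus 0 and p = 0.042 for 5 versus 0. The smallest significant difference is therefore 5/15 = 33 percentage points. For a quantitative outcome, the t-test approximation needs an observed difference of about 2.05 × √(2/15) = 0.75 SD. Unless the true effect is about that large, a significant estimate will tend to exaggerate it.

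**The case against.** The strongest reply is that this is a pilot. It announces no confirmatory claim, and no decision rule depends on a p-value. Latency is already the working lead outcome. That stands, and it limits the consequence: this is an improvement to claims and reporting, not a flaw that invalidates the design. It does not remove the point, because the objective includes the effect on all the outcomes and the plan attaches a significance level to them without limit.

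Four stronger readings are tempting, and the documents do not support them:

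- **A false-positive chance near 50%.** That needs 14 independent tests of exact 5% size. Fisher's test at 15 per arm falls far short of 5%, and correlation is built in: gestational age at delivery is gestational age at rupture plus latency, and birth weight and neonatal stay depend on it.
- **No effect estimate is planned.** The plan includes a difference in mean latency and Kaplan-Meier curves by group. What is missing is narrower: confidence intervals, and between-group estimates for the other 13 outcomes.
- **Latency is tested twice at 5%.** It is analysed twice, but no log-rank or other test is named alongside the Kaplan-Meier curve.
- **A chance finding could decide the future trial's endpoint.** The plan already bases that trial's sample size on mean latency, although SAMPLE SIZE also mentions infection.

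**Conclusion.** The point holds. Fourteen outcomes share an unadjusted 5% level, with none primary and no exploratory label. The resulting chance of at least one false significant result is roughly 20–35%, and about 17% with very strong correlation; 51% is only the ceiling under independence and exact size. These figures depend on assumed event rates and correlations and on an even split of 15 per arm. The qualitative conclusion is less sensitive: even the lowest scenario examined, 16.6%, is more than three times 5%. Because this is a pilot with no declared confirmatory claim, the change is one that should be made rather than one on which the trial depends.

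**What to change.** - **OUTCOMES:** label latency as the single primary outcome, since it already sizes the future trial. Label chorioamnionitis as the key secondary outcome and the other twelve as secondary.
- **STATISTICAL ANALYSES, latency:** pre-specify either the Mann-Whitney or the survival comparison as the only test at 5%, with the other supportive. If the survival comparison is chosen, name its test. Add a 95% confidence interval to the planned difference in mean latency.
- **STATISTICAL ANALYSES, everything else:** report chorioamnionitis and all other outcomes as between-group effect estimates with 95% confidence intervals and no claim of significance. Say explicitly that this includes chorioamnionitis: two outcomes tested at 5% without an order would give up to 1 − 0.95² = 9.75% under independence.
- **No multiplicity correction is needed.** Bonferroni across 14 outcomes would set 0.05/14 = 0.0036 per test, which even a 7-versus-0 split (Fisher p = 0.0063) would miss.

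The cost is wording only: no added participants, data or procedures. The downside is that no significance claim can be made on a non-primary outcome, which a pilot of 30 women could not support anyway. The primary label protects the 5% level only if it is fixed before outcomes are compared by group.

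### Does the comparison of neonatal hospital stay need a stated rule for infants who die before discharge?

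*Combined protocol and SAP*

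**What the plan says.** The OUTCOMES section lists, among the neonatal outcomes, "length of hospitalization, neonatal sepsis, composite adverse pulmonary outcome (need for ventilatory support, respiratory distress syndrome, bronchopulmonary dysplasia), and neonatal death". Stay and death are thus two outcomes, and neither is defined in terms of the other. The STATISTICAL ANALYSES section has one general rule for continuous and ordinal measures, "Medians of quantitative variables compared by Mann-Whitney U test", under "Intention-to-treat analysis; significance level of 5" per cent. Survival methods are named for latency only. Nothing says when a stay ends or what value an infant who dies contributes.

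The study is a "Pilot unblinded randomized controlled trial (1:1 allocation ratio" with a simple random sequence, and on size the plan says "we aim a sample of 30 participants". The objective is to study "the impact of bed rest in latency time to delivery, chorioamnionitis incidence and other maternal and neonatal outcomes" so that a later trial can be sized, and the analysis section adds: "Sample size for future RCT calculated based on difference between the means of latency time".

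**The concern.** Rupture from 24 weeks is eligible and delivery may come before week 34, so very preterm birth and neonatal death are possible. The plan lists death as an outcome and so foresees it. A rank test on days in hospital then has an awkward property: an infant who dies on day 2 ranks with the infants who went home soonest. An arm with more early deaths would tend to look better on stay. Leaving out the deaths avoids that, but it compares survivors only, a group formed after randomisation.

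The intention-to-treat statement does not resolve this. It fixes the arm in which an infant is analysed, not the value recorded after death. The trial is also unblinded, so a rule chosen late could be chosen with results by arm in view. At stake is whether the stay p-value can be read as evidence about infant benefit.

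**Working it through.** **Inputs.** From the documents: 30 participants, 1:1 allocation (taken as 15 per arm), Mann-Whitney U, 5% level (taken as two-sided). The documents give no mortality rate, no timing of death and no distribution of stay, so everything on those points below is an assumption. The plan states no figure on this point to reproduce.

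**Null distribution.** E(U) = 15 × 15 / 2 = 112.5. SD(U) = √(15 × 15 × 31 / 12) = 24.11. Let k be the number of excess early deaths in one arm, with underlying stays equally distributed in the two arms.

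**Case (a): the infants who die would have had typical stays.** Each of the other 15 − k infants contributes 7.5 to U on average.

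- Observed days: z = (7.5(15 − k) − 112.5) / 24.11. For k = 1, −7.5 / 24.11 = −0.31; for k = 2, −15 / 24.11 = −0.62.
- Deaths dropped: z = 0 for both.
- Deaths ranked worst: add 15k to U. For k = 1, +7.5 / 24.11 = +0.31; for k = 2, +15 / 24.11 = +0.62.

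**Case (b): the infants who die would have had the longest stays.** The i-th ordered stay contributes 15i/16 on average.

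- Observed days: U sums to 98.44 (k = 1) or 85.31 (k = 2), so z = −14.06 / 24.11 = −0.58 or −27.19 / 24.11 = −1.13.
- Deaths dropped: the null mean is 7.5(15 − k) and the SD is √((15 − k) × 15 × (31 − k) / 12), which is 22.91 or 21.71. Then z = (98.44 − 105) / 22.91 = −0.29 or (85.31 − 97.5) / 21.71 = −0.56.
- Deaths ranked worst: (98.44 + 15 − 112.5) / 24.11 = +0.04 or (85.31 + 30 − 112.5) / 24.11 = +0.12.

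**Chance of a nominally shorter stay (z < −1.96) in the arm with the excess deaths, by simulation.** The reference with no deaths is 2.5%.

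| Rule | one death | two deaths |
|---|---|---|
| (a) observed days | about 4% | about 7% |
| (b) observed days | 8.0% | 19.6% |
| (b) deaths dropped | 5.2% | 8.8% |

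Under (a), ranking deaths worst gives about 4% and 7% in the opposite direction. Later deaths matter less: under (a) with observed days, z is −0.16 / −0.31 if death falls at the lower quartile of survivors' stays, and 0 at the median.

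**Is there a systematic error?** Those figures condition on an imbalance. Without conditioning, at equal mortality of 3%, 5% or 10% (assumed), the observed-days test rejects in 2.5% on each side. For two Binomial(15, p) counts, the arms differ by at least one death in 51%, 63% and 75% of trials, and by at least two in 10%, 19% and 35%, equally often in either direction. If true early mortality were 10% against 3% (assumed), the mean z is −0.33 with 5.0% nominally shorter under (a), and −0.62 with 8.6% under (b).

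**Would the death comparison show an imbalance?** Fisher's exact test with 15 per arm gives p = 0.100 for 4 deaths against 0 and p = 0.042 for 5 against 0. The counts can be read directly, but the test has little power.

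**Dependence on the split.** A simple random sequence need not give 15/15. If unrestricted, an exact 15/15 split has probability 14%, and a split of 12/18 or more uneven 36%. At 12/18, Fisher gives p = 0.018 for 4 against 0 in the smaller arm and p = 0.057 for 6 against 0 in the larger. The z values above hold for 15/15 only.

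**The case for a change.** The best case for a change is that a rule costs a sentence or two and no data, and that a reader of the stay p-value cannot tell which rule produced it. Separate reporting of deaths helps only partly, since the death comparison is so weak at this size. If the infants who die would have had long stays, which is plausible among very preterm infants, both observed days and survivors-only flatter the arm with more deaths, while ranking deaths worst is nearly neutral (+0.04 / +0.12).

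What stands is that the rule is unwritten and that stay could be misread if early deaths fell unevenly. What does not follow is that the plan is in error. Worst rank is near neutral only under case (b). Under case (a) it moves the comparison by the same amount as observed days, with the sign reversed, and it carries mortality, already an outcome of its own, into the stay comparison. Whether that is wanted depends on whether stay is meant as infant benefit or as bed use. Its place among the neonatal outcomes leans towards the former but does not settle it. For the bed-use reading, the rule one would write is observed days for all infants with deaths alongside, which is the plan as it stands. A rule for infants who die would also not clearly cover a pregnancy with no live birth, so the proposed wording would not close the gap.

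**Conclusion.** No change is called for. This is a gap that an analyst fills sensibly from the text: all infants in their randomised arm, days in hospital as observed, deaths tabulated by arm next to them. Intention to treat makes dropping the deaths the less natural reading, though it does not strictly rule it out.

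Read that way, the test has its nominal 2.5% per side whenever mortality and timing of death are the same in both arms. A systematic distortion needs a difference that the documents give no reason to expect; even an assumed 10% against 3% raises the one-sided rate only to about 5% under (a) or 8.6% under (b). A chance excess of one or two early deaths can shift a single result by z between −0.31 and −1.13, depending on k and on who dies, but such an excess falls on either arm equally often and is visible in the death counts. These sizes assume exactly 15 per arm and deaths early enough to rank below every survivor.

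The consequence is confined to one of several neonatal outcomes in a 30-participant pilot. The calculation that the pilot exists to support uses latency and is unaffected. When results are written up, stating how deaths were counted and giving survivors' median stay beside them is ordinary good reporting and needs no amendment.

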## **BACKGROUND**

Preterm premature rupture of the membranes (PPROM) is defined as spontaneous rupture of the membranes before labor at less than 37 weeks of gestation. It complicates 3 percent of pregnancies but is responsible for one third of cases of preterm birth, which is the leading cause of perinatal morbidity and mortality in developed countries. PPROM etiology is still unclear but underlying infectious process, increased inflammatory pathway activation and genetic predisposition are probably involved. Latency time from PPROM to delivery is usually brief and inversely proportional to gestational age (GA) at rupture. During this time, intrauterine infection, placental abruption, umbilical cord compression or prolapse, and fetal compression and hypoxia are possible consequences. Chorioamnionitis is the major maternal consequence of PPROM. Neonatal morbidity is also higher when PPROM is complicated by chorioamnionitis but prematurity remains the major neonatal consequence after PPROM. Several studies support that prolonged latency improves fetal maturation and does not worsen neonatal prognosis, for a given GA at birth. In order to increase GA at birth, expectant management of viable pregnancies with prophylactic antibiotic administration is recommended. Antepartum bed rest is also widely prescribed, although its effectiveness to prevent preterm birth has not been demonstrated.

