## **POPULATION**

Eligible patients include those with single pregnancies with PPROM at  $24^{+0}$ - $33^{+6}$  weeks of gestation admitted to our tertiary center.

PPROM diagnosis on the basis of patient's history and sterile speculum examination with visualization of amniotic fluid pooling in the vagina and/or leaking from the cervical canal.

Exclusion criteria: indication for immediate delivery on admission (chorioamnionitis, placenta abruption, cord prolapse, signs of fetal hypoxia/distress), fetal malformations, multiple gestation, and maternal immunosuppressive disease.

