## **INTERVENTION**

Bed rest vs activity: Activity restriction group with motion limited to bathroom privileges and walks to the ward canteen four times per day. Participants on complete bed rest group keep antepartum confinement to bed with toileting restricted to bedpan use. Participants in this group receive prophylactic subcutaneous enoxaparin (40mg/day).

All patients receive standard care for PPROM according to the institution protocol, including hospital admission, antibiotic prophylaxis (ampicillin IV 2mg/4id plus erythromycin IV 500m/4id for 48h, followed by amoxicillin PO 500 mg/3id plus erythromycin PO 500 mg/3id for 5 days), fetal lung maturation (betamethasone IM 12mg/d for 48h), leucogram and C reactive protein (CRP) analysis (daily for 1 week and thrice weekly after), nonstress tests daily, and weekly ultrasound assessment (biophysical profile and flowmetry).

Delivery is planned for 34th week. In case of spontaneous labor or adverse occurrence (chorioamnionitis, abruptio placentae, signs of fetal hypoxia/distress) it can occur earlier. Mode of delivery respected obstetrical indications.

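### Latency is compared without adjustment for gestational age at rupture in 30 simply randomised women: a valid comparison, but precision may be lost and a chance imbalance can move the one mean difference observed

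*Combined protocol and SAP*

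**What the plan says.** The Statistical Analyses section gives the latency analysis in one sentence: "Latency from PPROM to delivery compared by univariate analysis using Mann-Whitney U test and by survival analysis using Kaplan-Meier curve with group stratification". I read the stratification as one curve per arm, because no GA strata are defined and no covariate model is named anywhere.

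On the use of the result, the same section says: "Sample size for future RCT calculated based on difference between the means of latency time". The Sample Size section puts it differently: "Considering future sample size calculation based upon assumed differences between groups regarding latency and infection, we aim a sample of 30 participants". The documents do not say whether the sizing difference is the one observed in the pilot or one assumed in advance. Sizing is central, because the stated objective ends: "thus enabling proper sample size calculation for future powered randomized controlled trial".

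Three other sections bear on GA:

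- Background: "Latency time from PPROM to delivery is usually brief and inversely proportional to gestational age (GA) at rupture". No slope, correlation or SD is given.
- Population and Intervention: rupture from 24+0 to 33+6 weeks is eligible, and delivery is planned for the 34th week unless labour or an adverse event comes first.
- Study Design: "Simple random allocation sequence generated by the investigators and implemented by sequentially numbered sealed envelopes". No blocking or stratification is described.

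**The concern.** GA at rupture acts on latency in two ways. The protocol itself calls it prognostic, and the planned delivery date limits how long each woman's latency can be. It is known for every participant, since eligibility depends on it. Leaving such a variable out of a 30-woman comparison can waste information. It also leaves the estimate exposed to the particular GA imbalance that chance produces. If the observed difference is then used to size the next trial, the shift goes with it. In addition, the two named latency methods give a rank comparison and curves, whereas the sizing rule needs a difference in means and an SD.

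**Working it through.** **The plan's own figure.** The target of 30 comes with no effect size, SD or power, so it cannot be reproduced. For context, take 15 per arm, two-sided 5% (sidedness is assumed) and 80% power. The detectable difference is (1.960 + 0.842) × √(2/15) = 1.02 SD. Precision is scarce.

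**The ceiling.** 24+0 is day 168 and 33+6 is day 237, a span of 69 days. If planned delivery is taken as 34+0, day 238 (an assumption), the longest possible latency falls from 70 days to 1 day across the eligible range.

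**How often GA is unbalanced.** With 15 per arm, the standard error of the difference in mean GA is SD × √(2/15) = 0.365 SD. For uniform GA, SD = 69/√12 = 19.9 days and the standard error is 7.3 days. The chance of a gap above 7 days is then 2[1 − Φ(7/7.27)] = 34%. Simulated simple randomisation, which allows unequal arms, gives:

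| Assumed GA distribution | SD (days) | SD of difference in means | Gap above 7 days |
|---|---|---|---|
| Uniform | 20.2 | 7.5 | 35% |
| Rising linearly | 16.6 | 6.2 | 26% |
| Bell-shaped around 30+5 | 12.5 | 4.6 | 13% |

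**Precision by formula.** With correlation ρ between GA and latency, adjusted variance / unadjusted variance ≈ (1 − ρ²)(1 + 1/26). This gives 1.04 at ρ = 0, 0.997 at 0.2, 0.95 at 0.3, 0.78 at 0.5 and 0.53 at 0.7. Break-even is at ρ² = 1/27, so |ρ| ≈ 0.19.

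**Precision by simulation.** All inputs are assumed: 30 women, the three GA distributions above, and exponential latency cut at 34+0. Median latency from 24+0 to 33+6 is 14 falling to 5 days, 10 throughout, or 20 falling to 4.

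- No effect: the unadjusted/adjusted variance ratio is 1.03-1.38. GA explains 7-28% of the variance, and the formula agrees roughly: 1/(0.93 × 1.038) = 1.04 and 1/(0.72 × 1.038) = 1.34.
- No effect, shorter assumed medians (3-7 days, in keeping with the Background's description of latency as usually brief): about 0.96-1.10.
- No GA relation and no ceiling: 0.96.
- Assumed hazard ratio 0.4: 1.13-1.66, with the top figure from the steepest GA pattern.

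At no effect, 30 women analysed by an unadjusted mean difference are therefore worth between 30/1.38 ≈ 22 and 30/0.96 ≈ 31 analysed with adjustment. The ends are not hard limits. Weibull latency gives 1.02-1.44. Letting latency scale with the time left to 34 weeks gives up to 1/0.71 = 1.41.

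**Shift from a 7-day gap in mean GA.** At no effect it is 1.0-2.5 days in the main scenarios and 0.1-0.9 day with the shorter medians. The time-left model reaches 3.3 days. At hazard ratio 0.4 it is 1.9-3.5 days, against true differences of 5.8-9.2 days. After adjustment it is under 0.1 day in the main scenarios.

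**Validity.** In the main scenarios, type I error is 4.7-5.0% for Mann-Whitney and 4.7-5.1% for the linear model, whose 95% CI covers 94.4-95.3%. Among randomisations with a gap above 7 days only, Mann-Whitney rejects a true null in 5.5-9.8% and the linear model in 4.0-5.1%.

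**Sizing.** At hazard ratio 0.4, sizing from the observed difference is more than twofold wrong, or has the wrong sign, in 56-67% of pilots unadjusted and 52-58% adjusted. Within a scenario the gain is 3-9 percentage points. With the difference fixed in advance and only the residual SD taken from the pilot, the figure is 2-5%.

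**The case against.** The strongest reply is that nothing is broken. The trial is a pilot with no power claim, randomisation keeps the unadjusted comparison valid, and the gain from adjustment rests on assumed inputs and may be nil. That is right as far as it goes. It limits the severity, and it is why a 3% gain cannot be called a floor.

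A second reply is that the larger figures need a strong effect, while the documents state none. This also stands: the 66% applies only with hazard ratio 0.4 and the steepest GA pattern.

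Third, a power comparison can flatter adjustment. At hazard ratio 0.4, Mann-Whitney has 22-33% power and the linear model 32-43%, but that contrast also changes ranks to means. With an unadjusted t-test in between (23-37%), GA adjustment accounts for about 4-10 points and leaving ranks for about 1-6.

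Fourth, a linear model for skewed, capped latency need not displace the planned methods, and the protocol names no main analysis. I accept that; the model belongs beside them.

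What survives is narrower. The protocol names a prognostic variable, records it for every woman, does not balance it and does not use it. The likely gain exceeds the small cost unless GA and latency are nearly unrelated in the observed range.

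**Conclusion.** The point holds as a matter of precision and of the reliability of one realised estimate. At no effect, the variance of the unadjusted mean difference is between about 4% smaller and about 38% larger than the adjusted one. A 7-day GA gap moves the raw difference by about 0.1-2.5 days. These sizes depend on assumed GA distributions, latency patterns and a ceiling at 34+0; the documents supply only the direction of the relation.

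A reader might infer two stronger things, and the documents support neither. One is that the planned latency tests are biased or invalid: across randomisations they are not. The other is that adjustment would repair the sizing of the future trial. The harm to sizing arises only if the observed difference is used, and the Sample Size section may mean an assumed one. Even where the observed difference is used, adjustment removes only a small part of the error. Severity is minor to moderate.

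**What to change.** Add to Statistical Analyses, keeping Mann-Whitney and Kaplan-Meier as planned:

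> Days from PPROM to delivery will also be analysed by a linear model with arm and GA at PPROM in days (continuous), by intention to treat. The adjusted mean difference, its 95% CI and the residual SD will be reported, with the marginal SD alongside.

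State in the same section which difference sizes the future trial:

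- If it is an assumed difference, take only the SD from the pilot.
- If it is the observed difference, use the adjusted one with its CI, and say that adjustment does not make a 30-woman difference a reliable basis for sizing.
- In either case, use the residual SD if the future trial will adjust for GA and the marginal SD if it will not.

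The cost is a few sentences, one standard model and one degree of freedom, using a value already recorded for eligibility. If GA proves unrelated to latency, the adjusted variance is about 4% larger. Recruitment, allocation and care do not change.
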